#### Contact Information:

Protocol Registrar [contact]

Protocol Registrar [contact]

Protocol Registrar E-MAIL ([[contact]](mailto:[contact]))

\*Protocol Registration is open from 8:30 AM - 4:00 PM, Monday-Friday.

4. Fax/e-mail ALL eligibility source documents with registration. Patients **will not** be registered without all required supporting documents.

Note: If labs were performed at an outside institution, provide a printout of the results. Ensure that the most recent lab values are sent.

To complete the registration process, the Registrar will:

- assign a patient study number
- Randomized Group Assignment
- register the patient on the study

#### **4.2 Methods**

#### **Compare activation of ADRB2/PKA/BAD signaling pathway in the prostate glands of men who take or do not take ADRB2-selective beta blockers**

##### **Patients scheduled for prostate biopsy.**

The research staff screens the OR and clinic schedules for potential patients and provides a list to the investigator. [name] or co-Investigator will discuss the study with the patient and inform the research nurse or coordinator (research staff) about the patients who agreed to participate in the study. Research staff will inform Tissue Procurement Lab (Director [name]; [name], Tumor Procurement Coordinator) and courier about the scheduled date and time when prostate samples will be collected.

On the day of sample collection [name] lab will prepare box with dry ice for prostate biopsy samples, a box with wet ice for blood samples as well as 2 ml cryovials (Corning, cat#430488) to collect biopsies and tubes to collect blood (Na heparin, green-capped tube, 10 ml total blood volume).

Courier will pick up boxes from Tissue Procurement Lab (Director [name]; [name], [contact]) and deliver to research staff at Charlois clinic ([name]).

Recruited patients scheduled for prostate biopsy will be randomized into two groups. Group one will receive 40 mg propranolol given by research nurse 2 hours prior to prostate biopsy. The research nurse should withhold drug and contact treating physician if SBP <120 or HR < 63. Group two will receive no treatment.

All patients will fill out stress surveys on the biopsy day.

All patients will give approximately 10 mL of blood approximately 20 min prior to prostate biopsy to test plasma catecholamine levels (collected in 10 mL green top tube (sodium heparin) and sent on ice within 1 hour to clinical lab for processing) and propranolol level (collected in 10 mL green top tube (sodium heparin) and sent on ice to The Tissue Procurement lab for processing and storage as described below). For group one that takes propranolol, this blood sample will be drawn at 1.5 -2 hours after taking the propranolol tablet.

For the biopsy, at least 1 core of the prostate specimen is to be flash frozen (on dry ice -80C) for laboratory analysis. Each biopsy sample will be collected into separate cryovials. The samples will be picked up by courier at Charlois clinic and delivered to Tissue Procurement laboratory.. The tissue samples will be frozen at -80 C.

At Tissue Procurement Lab, the blood sample will be centrifuged to prepare plasma. Plasma will be transferred into cryovials and stored at -80 C.

### **Patients scheduled for prostatectomy.**

Research staff will inform Tissue Procurement Lab (Director [name]; [name], Tumor Procurement Coordinator) about the scheduled date and time when samples from prostate cancer patients will be collected at OR. Prior to the day of sample collection at specified time [name] lab will provide vials and freezing media to collect prostatectomy samples and plasma samples (Na heparin, green cup).

Recruited patients scheduled for prostatectomy will be randomized into two groups. Group one will receive 40 mg propranolol given by research staff 2 hours prior to prostatectomy. The research staff should withhold drug and contact the study physician performing the procedure and/or the anesthesiologist if SBP <120 or HR < 63. Group two will receive no treatment. All patients will fill out stress surveys prior to prostatectomy.

Research staff will collect stress questionnaire and will collect blood into the vials with Na heparin that will be stored on ice (+4C). All patients will give approximately 10 ml of blood approximately 20 min prior to prostatectomy to test plasma catecholamine levels and propranolol level. For group one that takes propranolol, this blood sample will be drawn at 1.5 -2 hours after taking the propranolol tablet. Blood will be collected into two 10 mL green top (sodium heparin) tubes. One tube will sent on ice within 1 hour to the clinical lab for processing of fractionated catecholamines. The other tube will be sent on ice to The Tissue Procurement lab for processing and storage. The plasma will be separated, transferred to cryovials, and stored in -80C at the Tissue Procurement Lab

Prior to anesthesia patient will be evaluated by anesthesiologist for hypotension and bradycardia. Prostatectomy samples will be collected by Tissue Procurement Coordinator and placed into cryovials and flash-frozen. At least 3 vials with the prostate specimens will be flash frozen (on dry ice -80C) for laboratory analysis and stored at the Tissue Procurement Lab.

Prostate samples will be analyzed for the overall status of prostate tissue (by pathologist) and for activation of ADRB2/PKA signaling pathway .

Analysis of ADRB2/PKA signaling pathway will be conducted by two methods: 1) western blotting to measure phosphorylation of CREB and BAD; 2) analysis of mRNA expression signature that reflects activation of ADRB2/PKA signaling pathway. Methods related to western blotting of material and RNA analysis will be per manufacturer's instructions with modifications to adapt the protocol to the particular conditions of the experiments and will be kept in laboratory notebooks in the analyzing laboratory. Results will be kept in laboratory notebooks, but will also be recorded on the associated data collection forms (Appendices J-M) where appropriate and will ultimately be entered into a REDCap database.

**Experimental plan ([name] laboratory):**

1. Test whether LCM can be used to excise epithelial cells from frozen sections of prostate tissue for analysis of CREB and BAD phosphorylation by Western blotting, and for the analysis of mRNA by qPCR or RNA seq.
2. Recruit patients prior to prostate biopsy or prostatectomy. We plan to recruit 60 patients to this study and expect that 10 patients may not have evaluable tumor tissue. Patients will provide medical history and pre-study blood samples. On the day of prostate biopsy, the patients will fill out two stress surveys, being given propranolol or no treatment approximately 2 hours prior to biopsy or surgery, give blood, have prostate biopsy/prostatectomy, at which point prostate sample will be collected.
3. Compare CREB phosphorylation, BAD phosphorylation in prostates of men who took and who did not take propranolol. Based on our recent study of activation of ADRB2/PKA pathway in prostate biopsies we anticipate that in ~ 20% patients (10 of 50) ADRB2 pathway will be activated . If the selective beta blocker propranolol inhibits ADRB2/PKA pathway, then we will not see CREB and BAD phosphorylation in prostates of patients who take propranolol. In the no treatment group, patients are expected to show elevated BAD and CREB phosphorylation in their prostates. The levels of CREB and BAD phosphorylations will be determined by probing Western blots with antibodies to pS133CREB and total CREB; pS112BAD and total BAD. Ratios of signals from pS133CREB/total CREB and pS112BAD/total BAD will be used to compare CREB and BAD phosphorylations in prostate tissue samples.
4. Free plasma propranolol (pharmacologically active) will be measured at The Proteomics and Metabolomics Shared Resource (Dir. [name]) using chromatographic separation and fluorometric detection (linear detection range 5-400 µg/L) as described in .
5. Using prostate cancer cell models and tissues from the tumor bank, we will test if there is an mRNA signature of activation of ADRB2/PKA signaling pathway.

6. Compare mRNA signature of activation of ADRB2/PKA signaling pathway in prostates samples of men who take propranolol versus those who take nothing. Analysis of forskolin-induced genes using Affimetrix platform has been reported for HEK293T, MIN6 cell lines and primary hepatocytes and identified respectively 6, 14 and 17 mRNA transcripts induced over 3 fold. These results suggest that it would be possible to identify transcripts induced by ADRB2/PKA signaling in prostate cells as well. Our pilot studies identified 8 transcripts induced in prostate cells by epinephrine. Experiments to confirm the specificity of these transcripts for ADRB2/PKA signaling pathway are currently ongoing.

Results of these experiments will inform whether blood epinephrine levels can be determined above which ADRB2/PKA pathway is activated in prostate cells; whether beta blockers inhibit activation of ADRB2/PKA pathway in prostates and which method of monitoring activation and inhibition of ADRB2/PKA pathway is most adequate for analysis of clinical samples.

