### **2.2 Secondary Objectives**

- 2.2.1 To compare activation of ADRB2/PKA/BAD signaling pathway in the prostate glands of men two hours after taking or not taking propranolol prior to prostate biopsy or prostatectomy as indicated by phosphorylated BAD.
- 2.2.2 To determine the difference in candidate transcript levels associated with ADRB2/PKA activation between individuals two hours after taking propranolol or not taking propranolol prior to prostate biopsy or prostatectomy.
- 2.2.3 To determine plasma propranolol levels in individuals taking propranolol two hours after administration prior to prostate biopsy or prostatectomy.
- 2.2.4 To determine if plasma catecholamine levels in men with prostate cancer can be used as a biomarker to identify patients who show activation of ADRB2 signaling pathway in prostate tumors.

- 2.2.5 To determine perceived stress level differences in men with prostate cancer prior to prostate biopsy or prostatectomy to examine possible association between perceived stress level and catecholamine levels in blood and activation of ADRB2 pathway in tumors
- 2.2.6 To determine perceived distress level differences in men with prostate cancer prior to prostate biopsy or prostatectomy to examine possible association between distress level and catecholamine levels in blood and activation of ADRB2 pathway in tumors.

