## **3.0 Study Population**

Patients recruited will be individuals scheduled for prostate biopsy or prostatectomy. For this study, 60 individuals will be recruited. Patients will be randomized to receive the treatment (or not) for a total of 30 patients receiving propranolol prior to biopsy or prostatectomy and 30 patients receiving no treatment. It is expected that approximately 10 (5 patients in each group) may have non-evaluable tumor tissue. In case the number of evaluable tumors will be less than 25 for each group, more patients will be recruited to accumulate 25 evaluable samples for each group.

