## 8.0 Analytic Plan

### 8.1 Power Calculation/Sample size

Based on the preliminary data, the baseline level of CREB phosphorylation was 0.73 with a standard deviation of 0.26 . Using these values, we determined that there is 80% power to detect a difference of 0.21 between groups using a 2-sample t-test (alpha=0.05, 2-sided). Thus, if the control group has a value of 0.73 (based on the preliminary data) then we would be able to detect a difference if the value of CREB phosphorylation is below 0.52. Based on the preliminary data, this effect size is 0.81, and would correspond to a 29% relative change in CREB phosphorylation. This calculation is based on have 25 patients in each group being evaluable (i.e., having tumor tissue available to be evaluated).

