### 8.2 Primary Objective

Since this is a randomized trial, the two groups can be compared for CREB phosphorylation levels using a two-sample t-test. In addition to the 2-sample t-

test, descriptive statistics will be calculated for this primary outcome within each group. These statistics include n, mean, standard deviations and 95% confidence intervals.

Based on the preliminary data, the baseline level of CREB phosphorylation was 0.73 with a standard deviation of 0.26 . Using these values, we determined that there is 80% power to detect a difference of 0.21 between groups using a 2-sample t-test (alpha=0.05, 2-sided). Thus, if the control group has a value of 0.73 (based on the preliminary data) then we would be able to detect a difference if the value of CREB phosphorylation is below 0.52. Based on the preliminary data, this effect size is 0.81, and would correspond to a 29% relative change in CREB phosphorylation. This calculation is based on have 25 patients in each group being evaluable (i.e., having tumor tissue available to be evaluated). Sixty patients are to be enrolled to allow up to 10 patients (5 per group) to possibly not have evaluable tissue available at the time of analyses.

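### The expected 10 activated men of 50 become about 5 of 25 untreated men if propranolol works, and no analysis set is named for relating catecholamines, stress and distress to activation

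*Combined protocol and SAP*

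**What the plan says.** Section 4.2, laboratory experimental plan, item 3, carries over a rate from the group's earlier biopsy study: "we anticipate that in ~ 20% patients (10 of 50) ADRB2 pathway will be activated". The 50 are the evaluable men of both arms. Section 3.0 allocates 60 men equally, and Section 8.1 states "This calculation is based on have 25 patients in each group being evaluable". Item 3 goes on to say that if the drug inhibits the pathway, "then we will not see CREB and BAD phosphorylation in prostates of patients who take propranolol". For the other arm it says "In the no treatment group, patients are expected to show elevated BAD and CREB phosphorylation in their prostates", without giving a proportion.

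Objective 2.2.4 asks whether plasma catecholamines "can be used as a biomarker to identify patients who show activation of ADRB2 signaling pathway in prostate tumors". Objectives 2.2.5 and 2.2.6 ask whether perceived stress and distress are associated with catecholamines and with activation. The unnumbered paragraph that closes the laboratory plan, after item 6, says the experiments will inform "whether blood epinephrine levels can be determined above which ADRB2/PKA pathway is activated in prostate cells". None of these is limited to one arm.

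Catecholamines are measured in all patients. In Group 1 the sample is drawn 1.5 to 2 hours after the tablet (Section 4.2). For all six secondary objectives, Section 8.3 plans two-sample t-tests between the randomized groups plus descriptive statistics. It names no association analysis, no analysis set for one, no cut-off for activation and no adjustment for treatment.

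**The concern.** Ten activated men among 50 requires a 20% rate in both arms, while the trial's hypothesis puts the rate in one arm near zero. A team planning the biomarker work around ten activated men may have about half that number to work with.

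The second issue is who enters the analysis. The biomarker question is whether a man's catecholamine level tells us that his pathway is active. Propranolol acts between the two: it blocks the receptor through which epinephrine leads to pCREB. A treated man with high epinephrine and no pCREB shows that the drug worked. In an unadjusted analysis of all men he is scored as a false positive for the biomarker. The better the drug works, the worse the marker looks, so a useful marker could be dismissed or an epinephrine threshold misplaced. Nothing in the plan rules this analysis out, and the one analysis it does specify, the between-arm t-test, does not answer the question.

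**Working it through.** **Inputs from the documents.** Activation rate about 20%, 10 of 50 (Section 4.2, item 3). Evaluable men 25 per arm (Sections 3.0, 8.1, 8.2). Primary power: difference 0.21, SD 0.26, two-sided alpha 0.05 (Section 8.1).

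**Inputs that are assumptions.** The documents give no accuracy for catecholamines as a marker, no degree of blockade and no activation cut-off. The values below are illustrations. They also assume the drug does not itself shift catecholamine levels.

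**1. The plan's own figures.** 0.20 × 50 = 10, as stated. A two-sample t-test with 25 per arm has 79.9% power (noncentral t), which agrees with the stated 80%.

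**2. Activation that can be observed.** Let r be the share of activation that persists under treatment.
- Untreated arm: 0.20 × 25 = 5. Treated arm: 5r. Total: 5 + 5r.
- r = 0 gives 5; r = 0.25 gives 6.25; r = 0.5 gives 7.5; r = 1 gives 10.
- The 95% binomial range for the untreated arm is 1 to 9 activated men. P(2 or fewer) = 0.8^25 + 25(0.2)(0.8^24) + 300(0.04)(0.8^23) = 0.004 + 0.024 + 0.071 = 0.098.

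**3. Precision for a yes/no analysis.**
- When all n activated men test high, the exact 95% lower limit on sensitivity is 0.025^(1/n): 48% for n = 5 and 69% for n = 10.
- An AUC of 0.80 has a Hanley-McNeil standard error of 0.127 with 5 versus 20 men, against 0.089 with 10 versus 40.

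**4. Effect of combining arms without adjustment: worst case.** Take a marker that is perfect in untreated men, with full blockade.
- Group 2: 5 of 25 high, all activated. Group 1: 5 of 25 high, none activated.
- Untreated only: predictive value 5/5 = 100%, specificity 20/20 = 100%.
- All men: predictive value 5/(5 + 5) = 50%, specificity (20 + 20)/(20 + 25) = 40/45 = 89%.
- Half of activation persisting (r = 0.5): predictive value 7.5/10 = 75%, specificity 40/42.5 = 94%. With r = 1 there is no loss.

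**5. The same with a less ideal marker and full blockade.**
- Sensitivity and specificity both 0.80. Untreated predictive value is 4/(4 + 4) = 0.50. Over all men, false positives are 40 × 0.20 + 5 × 0.80 = 12, so predictive value is 4/16 = 0.25 and specificity 33/45 = 0.73.
- AUC of 0.80: (40 × 0.80 + 5 × 0.50)/45 = 0.77, a modest loss.
- Activated men 1.5 SD higher in catecholamines. The correlation with activation is 1.5 × 0.4/√1.36 = 0.51 in untreated men and 0.08 × 1.5/√(1.36 × 0.09) = 0.34 over all men.

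**The case against.** Several stronger readings are tempting, and the documents do not support them.

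- A reader might infer that the plan pools the arms for 2.2.4 to 2.2.6. It does not say so; it specifies no association analysis at all. The distortion in steps 4 and 5 is therefore conditional.
- A reader might infer that any analysis of all men is invalid. It is not. A model with treatment and a treatment-by-catecholamine term uses both arms properly.
- A reader might take 10 of 50 as the promised yield for the biomarker objective. The figure stands in an item about comparing phosphorylation between arms and is tied to no power or precision claim for 2.2.4. It can also be read as the number who would be activated without drug, in which case item 3 is not strictly contradictory. Even so, only about 5 would show activation in tissue if the drug works.
- A reader might take full blockade as given. The dose-adjustment rule in Section 8.4 foresees phosphorylation persisting in treated men whose epinephrine exceeds 1 nM. That rule also reads Group 1 as evidence about inhibition, not about the marker, which counts against assuming that treated men would be scored as false positives. It is an interim rule, however, and does not govern the final analysis.
- The count of 5 limits only a yes/no analysis. The pCREB ratio is continuous (Section 8.1 gives mean 0.73, SD 0.26), and a continuous analysis would use all 25 untreated men. Objective 2.2.4 is nonetheless worded as identifying activated patients.

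It can also be said that naming the analysis set is simply part of specifying the missing association analysis. The two belong together, but adding a correlation over all 50 men would close one gap and leave the other open. These are secondary objectives in what Section 8.4 calls a pilot study, which limits the weight of the point.

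**Conclusion.** The concern holds as a gap in specification with a foreseeable consequence. It is not a demonstrated error of analysis. If the trial's hypothesis is true, about 5 of 25 untreated men are expected to show activation, or between 5 and 10 of 50 overall with partial blockade. This rests on the 20% rate from the cited biopsy study carrying over to a mixed biopsy and prostatectomy population.

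The objectives that link catecholamines, stress and distress to activation name no analysis set, and the planned t-tests do not address them. An unadjusted analysis of all men would be biased against the marker. At worst predictive value is halved and specificity falls by 11 percentage points; the AUC loss is about 0.03 in the example, and there is no bias if the drug has no effect. The sizes depend on the assumed marker accuracy, degree of blockade and a cut-off that the plan does not define. The primary comparison is not affected.

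**What to change.** - In Sections 2.2 and 8.3, state that the relation of catecholamines, stress and distress to pathway activation is estimated primarily in the no-treatment group, using the continuous pCREB ratio where possible. If an activated/not-activated split is kept, define the cut-off in advance.
- Show Group 1 separately, or include it only through a model with treatment and a treatment-by-catecholamine term. Apply the same population to the epinephrine-threshold aim that closes the laboratory plan in Section 4.2.
- In Section 4.2, item 3, restate the expectation as about 5 of 25 men showing activation in the no-treatment group. Reconcile this with the sentence that untreated patients are expected to show elevated phosphorylation.
- Label these estimates exploratory and report them with confidence intervals.

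The cost is wording only: no new data, no more patients and no change to the primary analysis. The downside is a less favourable stated yield and visibly wide intervals, both of which the design already implies.

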#### **Experimental plan (clinical):**

Prior to prostate biopsy or prostatectomy, a complete history and physical will be performed per standard of care; this can be completed during the initial consult. The necessary clinical information, including most recent PSA and testosterone if available (per standard-of-care) will be retrospectively obtained from what is charted and recorded per Appendix G.

Study related activities for the day of prostate biopsy or prostatectomy should be recorded on the Surgery Day Worksheet (Appendix N). Patients will fill out both the perceived stress form (Appendix C) and the Distress Thermometer (Appendix D). Patients will receive either propranolol 40mg po x1 or no treatment 2 hours prior to prostate biopsy or prostatectomy. Approximately 20 minutes prior to prostate biopsy or prostatectomy, Group 1 will have approximately 10 mL of blood collected into two green top (sodium heparin) tubes. Group 2 will have the same amount of blood collected into two green tops. There will be no time limit prior to the biopsy or prostatectomy. Plasma will be separated and stored for future analysis of propranolol levels.

Epinephrine (fractionated catecholamines) levels will be performed per standard clinical laboratory procedures on all patients.

Information regarding tissue and plasma collection will be recorded on the Tissue Collection Form (Appendix H) or the Blood Collection Form (Appendix I). All stored plasma or tissue will be stored in the Tumor Tissue Core.

Tumor Tissue Core  
Wake Forest Baptist Comprehensive Cancer Center  
Tumor Tissue Core Facility  
Care of [name]  
[name]

[name]  
[name]

